8.2. SECONDARY EFFICACY/PD ENDPOINT(S) AND ANALYSES

The main analysis population for secondary efficacy endpoints is the Efficacy Population. The analysis will also be repeated for the Per Protocol population and for subjects who completed their Week 24 assessment (completers) only.

8.2.1. The actual and percentage change from baseline in liver fat content by Magnetic Resonance Imaging-proton Density Fat Fraction. MRI-PDFF at Weeks 6, 12, 24, and 30

The observed values and changes from baseline will be summarized at Weeks 6, 12, 24, and 30, by NGM282 treatment group and fibrosis stage. The actual change and percentage change in absolute liver fat content from baseline to Week 6, Week 12, Week 24 and Week 30 will be compared between treatment groups using an analysis of covariance (ANCOVA) model with treatment group and fibrosis stage at baseline as cofactors and baseline endpoint and baseline ALT as covariates. Least square means with standard errors (SE), differences in least square means with SE, 95% CIs for the difference in least square means, and corresponding p-values will be presented.

The assumptions of normality will be evaluated. If the assumptions of normality are not satisfied, a rank ANCOVA method will be performed in addition to the parametric model.

The rank ANCOVA is a non-parametric statistical method described in Stokes, Davis, and Koch, 2000. It can be considered as an extension to the Wilcoxon rank-sum test with the ability to adjust for covariates and cofactors in the model. The mean, median and p-value for the actual change will be presented.

8.2.2. The percentage of normalization in absolute liver fat content at Week 24

Normal liver fat content normalization will be defined as $\leq 5.0\%$. Percent of subjects with normalized liver fat content will be presented by treatment group and fibrosis stage and will be analyzed through a chi-square test. The difference between proportions observed in each treatment group, along with 95% CIs for the difference between proportions, will be presented for all pairwise comparisons of treatment

Amendment Final V 2.0

groups. Fisher exact test will be used if 50% of the cells have expected counts less than 5.

8.2.3. The percentage of responders (based on a liver fat content decrease $\geq 5\%$, and relative decrease $\geq 30\%$)

The percentage of responders will be analyzed through a chi-square test. The difference between proportions observed in each treatment group, along with 95% CIs for the difference between proportions, will be presented for all pairwise comparisons of treatment groups. Fisher exact test will be used if 50% of the cells have expected counts less than 5.

[REDACTED]

[REDACTED]

[REDACTED]

8.2.4. The actual and percentage changes from baseline by Week 24 of AST, ALT, bilirubin (total, direct), triglycerides and GGT.

The actual and percentage changes from baseline will be summarized by treatment group. An ANCOVA model as stated in 8.2.1 will be used to compare between treatment groups.

In addition, the percentage of subjects with AST, ALT, Total Bilirubin, Direct Bilirubin, Triglycerides, and GGT lab measurements within the normal range will be summarized by lab parameter, treatment group and visit. All pairwise treatment group comparisons of the proportion of subjects within the normal range will be tested using a chi-square test. Fisher exact test will be used if 50% of the cells have expected counts less than 5.

[REDACTED]

8.2.5. The actual and percentage changes from baseline at Week 24 and EOS of the following parameters: Total cholesterol, HDL-cholesterol, LDL-cholesterol, and lipoprotein particles.

The actual and percentage changes from baseline will be summarized by treatment group and fibrosis stage. ANCOVA model as stated in 8.2.1 will be used to compare between treatment groups. The ANCOVA model as stated in 8.2.1 will be used to compare the two treatment groups.

Amendment Final V 2.0

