5. Other therapies for NAFLD or NASH: requires a stable regimen for at least 3 months prior to the Screening biopsy of record and throughout the study. May include vitamin E, milk thistle, thiazolidinediones and pentoxifylline.

Double-Blind Cohort:

Includes statins.

Open-Label Single Blind and Placebo Controlled 24 Week Histology Cohorts:

Includes statins if the conditions below are met. Other therapies may include vitamin E ( $> 800$  IU Placebo cohort only), milk thistle, thiazolidinediones (open-label, single-blind only) or pentoxifylline.

- a. Patient can be defined as statin naïve or experienced at Screening based on the following definitions:
  - i. **Statin-naïve:** no administration of statins within 3 months prior to enrollment.
  - ii. **Statin experienced:** administration of  $\leq 50\%$  of the maximal dose of current statin therapy.
- b. Requires a stable regimen for at least 3 months prior to Screening through Week 2.

The following are the acceptable daily doses of approved statin therapies, including combination preparations of statins and other lipid lowering agents. Also listed under Concomitant Medications in [Section 9.7](#).

- Atorvastatin:  $\leq 40$  mg/d
- Fluvastatin:  $\leq 40$  mg/d
- Lovastatin:  $\leq 40$  mg/d (immediate release),  $\leq 30$  mg/d (extended release)
- Pitavastatin:  $\leq 2$  mg/d
- Pravastatin:  $\leq 40$  mg/d
- Rosuvastatin:  $< 20$  mg/d (Note: must be  $<$  not  $\leq$  20 mg/d)
- Simvastatin:  $\leq 40$  mg/d

6. The following liver enzyme parameters must be met at Screening:
  - a. ALT and AST  $\leq 250$  IU/L
  - b. Abnormal ALT defined as:  $\geq 30$  IU in males and  $\geq 19$  IU in females
  - d. AST  $\geq 30$  IU/L except for patients with a historical biopsy within 3 months of screening with NAS of at least 4 with 1 point in each component and fibrosis stage 2 or 3 (Placebo-Controlled Cohort only)
7. The following additional laboratory parameters must also be met at Screening:

- a. Total bilirubin must be within normal range. For patients diagnosed with Gibert's Syndrome, please contact medical monitor/designee
  - b. INR  $\leq$  1.3 (in the absence of warfarin or other anticoagulant therapy)
  - c. Creatinine clearance  $\geq$  90 mL/min as calculated by Cockcroft-Gault equation
  - d. Alpha fetoprotein (AFP)  $<$  100 ng/mL
  - e. LDL C  $\leq$  185 mg/dL (except Double-blind cohort and  $\leq$  165 mg/dL for the Open-Label Single Blind )

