### **12.9.3 Analysis of Secondary Endpoints**

The analysis of secondary PD endpoints will be based on the Efficacy population, for all three cohorts separately.

For continuous secondary endpoints the same method of analysis as for the primary endpoint will be followed. Further covariates/cofactors may be included in the modeling depending on the relevance to the endpoint analyzed and will be further described in the SAP.

Categorical secondary endpoints (percentage of normalization) will be analyzed through a chi-square test. The difference between proportions along with 95% CIs for the difference between proportions will be presented by treatment-group comparisons.

The analyses in the open-label single-blind cohorts will be stratified by statin use at Baseline whereas they will be stratified by fibrosis stage in the placebo-controlled 24-week histology cohort. The effect of statin use on lowering LDL cholesterol will also be explored both the open-label single-blind and placebo-controlled 24-week histology cohorts. In addition, sensitivity analyses will be performed to investigate the effect on the efficacy endpoints of statin use in the open-label single-blind cohorts and fibrosis stage on the placebo-controlled 24-week histology cohort.

Comparisons between the 3 cohorts will be performed and further detailed in the SAP.

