4.2. SECONDARY EFFICACY ENDPOINTS

- The actual and percentage change from Baseline in liver fat content by MRI-PDFF at Weeks 6, 12, 24, and 30.
- The percentage of normalization in liver fat content at EOT.
- The percentage of responders
 - a liver fat content decrease $\geq 5\%$
 - a liver fat content relative decrease by $\geq 30\%$
- The actual and percentage changes from Baseline to EOT as well as the percentage of normalization of AST, ALT, bilirubin (total, direct), triglycerides and GGT. Percentage of normalization by Week 24 will be investigated for these parameters (including clinically meaningful normalization of Triglycerides)
- The actual and percentage changes from Baseline to EOT of the following parameters: Total cholesterol, HDL-cholesterol, LDL-cholesterol, and lipoprotein particles.
- The actual and percentage changes from Baseline to EOT of the following parameters: [REDACTED], Pro-C3, ELF Score, Fasting blood glucose, insulin levels, HbA1c, [REDACTED], and HOMA-IR, Body weight, BMI, and waist circumference, C4 and serum bile acids, Bile-mediated absorption as measured by fat-soluble vitamins and fecal fat content.
- The percentage of liver histologic responders
 - Improvement in liver fibrosis by ≥ 1 stage by NASH Clinical Research Network (CRN) criteria with no worsening of steatohepatitis
 - Resolution of NASH (defined as an NAS score of 0 or 1 for inflammation and 0 for ballooning) with no worsening of fibrosis as determined by the NASH CRN criteria.

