6. GENERAL ASPECTS FOR STATISTICAL ANALYSIS

6.1. GENERAL METHODS

Unless otherwise specified, for numeric data, descriptive statistics will include the number of subjects with data to be summarized (n), mean, standard deviation (SD), median, minimum (min), and maximum (max). The same number of decimal places as used in the raw data will be presented when reporting min and max, 1 decimal place more than in the raw data will be presented when reporting mean and median, and SD. If the raw data have 3 decimals or more, 3 decimals will be presented for the mean, median, min and max, and SD.

All categorical/qualitative data will be presented using frequency counts and percentages. All percentages will be rounded to 1 decimal point, with the denominator being the number of subjects in the relevant population, unless otherwise stated. Percentages equal to 100 will be presented as 100%; percentages will not be presented for zero frequencies but the categories whose counts are zero will be displayed for the sake of completeness.

Unless otherwise specified, all the tables will be summarized by treatment group (and overall, if applicable). All the listings will be sorted by treatment group, subject number and assessment date/time.

All confidence intervals (CIs) will be two-sided and will use 95% confidence levels. Any analyses requiring significance testing will use a two-sided test at the 5% significance level, unless otherwise specified.

In general, only data from nominal scheduled visits will be presented in the summary tables and figures unless otherwise specified. Data from unscheduled visits will not be summarized but will be presented in the data listings.

All analyses and outputs will be generated using SAS® version 9.4 (or higher).

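### As visible, SAP 8.2.4 tests laboratory normalization as the in-range share of all subjects with data, so subjects normal before dosing count as successes; for total bilirubin this defeats the endpoint

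*SAP*

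**What the plan says.** SAP 4.2 lists AST, ALT, total and direct bilirubin, triglycerides and GGT, and states: "Percentage of normalization by Week 24 will be investigated for these parameters". Protocol 12.9.3 supplies the method: "Categorical secondary endpoints (percentage of normalization) will be analyzed through a chi-square test".

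The only visible chi-square test for these parameters is in SAP 8.2.4. There "the percentage of subjects with AST, ALT, Total Bilirubin, Direct Bilirubin, Triglycerides, and GGT lab measurements within the normal range will be summarized" by parameter, arm and visit, and "All pairwise treatment group comparisons of the proportion of subjects within the normal range will be tested using a chi-square test", with Fisher's exact test for sparse tables. No baseline condition is visible. A redacted block follows.

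The denominator comes from elsewhere in the SAP:
- Section 8.2: "The main analysis population for secondary efficacy endpoints is the Efficacy Population". Section 5.3 defines that population without reference to baseline laboratory values.
- Section 6.1: percentages are formed "with the denominator being the number of subjects in the relevant population, unless otherwise stated".
- Section 6.3: no imputation, analysis of available data. In practice the denominator is Efficacy Population subjects with a value at the visit.

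Protocol 8.1.1 fixes some starting values. Criterion 7a: "Total bilirubin must be within normal range" (patients with Gilbert's syndrome are referred to the medical monitor). Criterion 6b calls for an abnormal ALT. Criterion 6d sets an AST floor "except for patients with a historical biopsy within 3 months of screening" that meets the histology conditions. No entry level is set for direct bilirubin, triglycerides or GGT.

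The parameter lists disagree. The efficacy criteria in the Protocol synopsis, and one sentence of SAP 3.2, confine normalization to ALT and triglycerides. Protocol 12.9.1, SAP 4.2 and SAP 8.2.4 cover all six. SAP 11 records no change from the protocol.

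**The concern.** To normalize is to move from abnormal to normal. The visible rule measures being normal at a visit. The two agree only if every subject starts abnormal. Liver fat meets that condition: entry needs at least 8%, and SAP 8.2.2 sets normal at 5.0% or less. The laboratory parameters do not meet it in general, and total bilirubin reverses it, since subjects must be normal to enter.

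At stake is what the reported difference means. It would carry the name normalization while mixing three things: abnormal subjects becoming normal, normal subjects staying normal, and chance imbalance between arms in how many began normal. Randomization is stratified by fibrosis stage only (Protocol 12.2), so that imbalance is left to chance.

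**Working it through.** **The plan's own figure.** The sample size rests on histologic response; neither document gives a rate or power for laboratory normalization. With 50% vs 15%, 80% power, two-sided 5% and 2:1 allocation (Protocol 12.1, SAP 3.5), the two-proportion formula without continuity correction gives 42 + 21 = 63 evaluable. Then 63/0.85 = 74.1, which rounds up to the planned 75. That figure is not in dispute, and 42/21 is used below.

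**What is tested.** Let q be the share normal at baseline, r the share of those still normal at Week 24, and p the share of abnormal subjects who normalize. The in-range rate in an arm is

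q·r + (1 − q)·p.

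With q and r equal in both arms, the tested difference is (1 − q)(p_drug − p_placebo).

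**Total bilirubin.** Almost all subjects start normal. Not strictly all: baseline is the last value on or before first dose (SAP 6.2.1), criterion 7a applies at Screening, and Gilbert's cases are handled individually. If q is 95% to 100%, about 0.05 × 63 = 3 subjects down to none could normalize. A 35-point effect would read as 0.05 × 35 = 1.75 points down to 0.

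**Other parameters: illustration only.** The one laboratory rate in the documents is that over half of subjects normalized ALT by Week 12 in the double-blind cohort (Protocol 5.7), so p_drug = 50%. Assumed: p_placebo = 15% (borrowed from histology planning), r = 95% in both arms, and the values of q. Power is by exact enumeration of both binomials, using the uncorrected chi-square test, or Fisher's exact test when at least two of the four expected counts are below 5. For the subset, the number abnormal at baseline is random (binomial in each arm).

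| q | In-range, drug vs placebo | Difference | Power, all subjects | Expected subset n | Power, abnormal at baseline |
|---|---|---|---|---|---|
| 20% | 59% vs 31% | 28 points | 60% | 34/17 | 72% |
| 40% | 68% vs 47% | 21 points | 39% | 25/13 | 57% |
| 60% | 77% vs 63% | 14 points | 23% | 17/8 | 32% |
| 80% | 86% vs 79% | 7 points | 11% | 8/4 | 8% |

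At an 80% share the subset test has no advantage.

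**Unequal retention, q = 50%.** With r = 95% on drug and 80% on placebo: 72.5% − 47.5% = 25 points. Reversed: 65% − 55% = 10 points. Equal retention would give 17.5, so the estimate can move either way.

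**Size under no effect.** With p equal in both arms at 15, 30 or 50%, r equal at 95 or 80%, and q from 10% to 95%, the all-subject test rejects 2.3 to 6.1% of the time. At q = 0 it rejects 4.0 to 6.1%, so including baseline-normal subjects adds no inflation. The subset test becomes very conservative at small n: 1.3 to 3.3% at 17/8 and under 1% at 8/4.

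**The case against.** **The redaction sits where a rule could be.** SAP 4.2 promises a clinically meaningful triglyceride criterion that is not visible in 8.2.4, so the hidden block may hold it or a further rule. The table index is redacted and the mock-ups are a separate document. This stands: the point is limited to the visible text, and a reader may not infer that the plan contains no definition.

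**The label is inferred.** The 8.2.4 paragraph does not use the word normalization; read alone, it describes an in-range comparison accurately. The link comes from joining SAP 4.2 to Protocol 12.9.3. But no other visible test could serve that endpoint.

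**Scope may be narrower.** If only ALT and triglycerides count, total bilirubin is not a normalization endpoint. ALT is then probably little affected, and triglycerides remain of unknown extent. That is a fair reading of two places in the documents, but three others say otherwise, and 8.2.4 tests bilirubin in any case.

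**The comparison is legitimate and partly backed up.** The in-range share at Week 24 among all treated subjects respects randomization and captures loss of normality. Each parameter also has a baseline-adjusted ANCOVA on change, and the SAP 9.3 shift tables separate becoming normal from staying normal. All true, but the shift tables are descriptive and the tested quantity still carries the wrong name.

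**Stronger readings to resist.** A reader might infer an invalid test or inflated type I error; the size calculation shows neither. A reader might infer material dilution for all six parameters; the documents show a defeated endpoint only for total bilirubin. A reader might extend the point to liver fat; the entry threshold rules that out.

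**Conclusion.** The point holds on the visible text, within limits. The documents themselves establish it for total bilirubin, where the rule measures staying normal. For direct bilirubin, triglycerides, GGT and AST the baseline-normal share is not given, so the extent is unknown. For ALT it is probably small, although the visible SAP does not tie its normal range to the protocol's entry cut-offs.

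The (1 − q) shrinkage is algebra and needs only equal baseline shares and equal retention. The power figures depend on assumed shares, assumed retention and a borrowed placebo rate, and should not be quoted as forecasts. The consequence is a mislabelled and often diluted secondary estimate. The primary endpoint is not touched.

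**What to change.** Unless the redacted text already does so:

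- In SAP 8.2.4, define normalization as outside the normal range at baseline (as in 6.2.1) and within it at Week 24. Test it among subjects abnormal at baseline for that parameter, and report their number by arm.
- Where few are abnormal at baseline, give only counts and a confidence interval.
- Keep the all-subject in-range share by visit as a descriptive summary.
- Do not test total bilirubin for normalization; rely on the SAP 9.3 shift tables.
- Reconcile the parameter list across the Protocol synopsis, Protocol 12.9.1 and SAP 3.2, 4.2 and 8.2.4, and record the change in SAP 11.

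The work is SAP wording plus one baseline filter on data already collected. The price is a smaller sample per parameter (about 17 vs 8 if 60% start normal), a conservative test at such numbers, and no formal test of any effect on keeping normal subjects normal. That last loss is the reason to retain the all-subject summary.

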### **9.6.8 Week 18 Procedures**

Subjects will report to clinic fasted and not dosed with NGM282. The following procedures will be performed:

Pre-dose:

- Conduct physical examination.
- Measure vital signs (including temperature, respiratory rate, and seated blood pressure and pulse).
- Record concomitant medications.
- Record new and/or changes to AEs.
- Obtain blood for 10-hour fasted clinical laboratory samples (if not fasted chemistries and lipid panel will need to be retested)
  - Results are blinded for ALT, AST, Total Cholesterol, LDL, HDL and triglycerides

In-clinic dosing and dispensing:

- Collect old NGM282 study-drug kit/diary and conduct reconciliation.
- Collect old rosuvastatin medication bottle/diary and conduct reconciliation.
- If subject is taking statins, evaluate tolerability and continue therapy to Week 24 for statin naïve or Week 30 for statin experienced
- Dispense new NGM282 study-drug kits (5) and diary.
- Dispense new rosuvastatin medication/diary.
- Oversee subject's NGM282 study-drug self-administration (from new kit).
- Perform LISSA evaluation.

Before clinic discharge:

- Remind subject to bring study drug kits/diary and to not self-inject NGM282 at home on clinic visit days.
- Schedule Week 24 (End of Treatment) visit and remind subject for home dosing to administer NGM282 or placebo as close as possible to the same time each day

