### **9.6.9 Week 24/Early Withdrawal (End of Treatment) Procedures**

Subjects will report to clinic fasted and not dosed with NGM282. The following procedures will be performed:

Pre-dose:

- Measure body weight, BMI, and waist circumference.
- Conduct physical examination.
- Obtain 12-lead ECG (after subject has been supine for at least 5 minutes).
- Measure vital signs (including temperature, respiratory rate, and seated blood pressure and pulse).
- Obtain blood and urine for 10-hour fasted clinical laboratory samples (if not fasted, chemistries and lipid panel will need to be retested)
  - Results are blinded for ALT, AST, Total Cholesterol, LDL, HDL and triglycerides
- Obtain an MRI assessment
  - MRI should be obtained before the last dose of NGM282 (standard Table 4 visit window applies)
- [REDACTED]
- Undergo a liver biopsy procedure to obtain new tissue
  - Results will be blinded.
  - Biopsy should be obtained before the last dose of NGM282 with a visit window of -7 days and +3 days

- Record concomitant medications.
- Record new and/or changes to AEs.

In-clinic dosing and dispensing:

- Collect old NGM282 study-drug kit/diary and conduct reconciliation.
- Collect old rosuvastatin medication bottle/diary and conduct reconciliation.
- If stain experienced subject is taking statins, evaluate tolerability and continue therapy to Week 30
- Statin naïve subjects taking statins are to discontinue therapy
- Dispense new rosuvastatin medication/diary to statin experienced subjects taking therapy
- Oversee subject's NGM282 study-drug self-administration (from old kit) (not applicable for Early Withdrawal subjects).
- Perform LISSA evaluation.

Before clinic discharge:

- Obtain 2-hour post-dose PK blood sample (except early withdrawal subjects).
- Schedule Week 30 (End of Study) Visit.

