7.2. DEMOGRAPHIC AND OTHER BASELINE CHARACTERISTICS

Demography (age, sex, race, ethnicity, type 2 diabetic status, cirrhosis status, cardiovascular event status, statin status, height, body weight, BMI and waist circumference at screening), will be summarized, by Steatosis score [Overall, 0 (< 5%), 1 (5%-33%), 2 (34%-66%) and 3 (> 66%)] and treatment group.

Individual data listings for demographic and baseline characteristics will be presented for each subject.

Age = (date signed informed consent - date of birth + 1) / 365.25 and truncated to complete years.

Height (cm) = height (inches) * 2.54

Weight (kg) = weight (lbs) * 0.4536

BMI (kg/m²) = Weight(kg)/[Height(m)²]

Previous Diagnoses including cirrhosis, diabetes, cardiovascular events/diseases, ..., etc. will also be summarized descriptively by presenting the number and percent of subjects reporting a history of each condition.

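### The pooled end-of-study lipid comparison mixes subjects taken off rosuvastatin with subjects who may still be on it; SAP 8.2.5 should also report lipids by baseline statin status

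*SAP*

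**What the plan says.** SAP 8.2.5 covers "The actual and percentage changes from baseline at Week 24 and EOS of the following parameters" (total cholesterol, HDL-C, LDL-C and lipoprotein particles). It summarises them by treatment group and fibrosis stage and takes its model from 8.2.1: "The ANCOVA model as stated in 8.2.1 will be used to compare the two treatment groups". The terms of that model are "treatment group and fibrosis stage at baseline as cofactors and baseline endpoint and baseline ALT as covariates". SAP 6.6 plans no subgroups. Protocol 12.10.2 also calls for inferential analysis of these lipids at both EOT and EOS.

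The rosuvastatin rules depend on baseline statin status. Protocol 10.4.2 gives separate algorithms for naive and experienced subjects, driven by LDL-C at Weeks 2, 4 and 8. Protocol 9.6.8 tells sites to "continue therapy to Week 24 for statin naïve or Week 30 for statin experienced". At Week 24, Protocol 9.6.9 adds: "Statin naïve subjects taking statins are to discontinue therapy".

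Statin status is already captured: SAP 7.2 lists "type 2 diabetic status, cirrhosis status, cardiovascular event status, statin status" among the baseline variables. Protocol 12.9.3 uses it in another cohort ("The analyses in the open-label single-blind cohorts will be stratified by statin use at Baseline") and names fibrosis stage for this one. The same section says that the effect of statin use on LDL cholesterol will be explored in both cohorts and leaves further endpoint-relevant cofactors to the SAP. SAP 3.2 lists the efficacy and safety of rosuvastatin as an objective.

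**The concern.** EOS is the only lipid time point after NGM282 has stopped, so a reader will take it as evidence on whether lipids recover. In naive subjects it is a washout from both drugs. In experienced subjects who took rosuvastatin it is a washout from NGM282 alone, with rosuvastatin continuing. Protocol 5.5 says that NGM282 raises LDL-C, and rises in LDL-C trigger rosuvastatin. More experienced subjects on NGM282 than on placebo may therefore still be taking study rosuvastatin at Week 30. The pooled difference would then look better for NGM282 because of the continued statin.

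Neither the fibrosis-stage summaries nor the terms of the 8.2.1 model can show this. Protocol 5.5 states that the clinical outcomes of long-term LDL-C elevation on this drug are unknown, so the reading of the off-drug lipids matters.

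**Working it through.** **Numbers available at EOS.** The documents give no SD, effect or power for any lipid. The cohort size comes from histologic response (50% v 15%, 80% power, two-sided 5%, 2:1, 15% dropout). With pooled proportion (0.15 + 2×0.50)/3 = 0.383:

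n(placebo) = [1.96·√(0.383×0.617×1.5) + 0.842·√(0.15×0.85 + 0.50×0.50/2)]² / 0.35² = 20.6, so 21.

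That gives 21 + 42 = 63 evaluable, and 63/0.85 = 74.1, so 75. The planned 50 + 25 is reproduced, and 42 v 21 is used below.

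**Assumed inputs (not in the documents).**
- Share statin-experienced p: 30–45%. For reference, the open-label cap of 8 in 25 is 32%.
- Experienced subjects on study rosuvastatin at EOS: 60% NGM282 v 20% placebo (low case); 80% v 30% (high case).
- Effect of rosuvastatin on LDL-C change from baseline in those subjects: -20 to -40 mg/dL.
- Residual NGM282 effect at EOS: none.

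**Step 1: what the pooled contrast estimates.** Naive subjects are off rosuvastatin in both arms, so their arm difference is 0. In experienced subjects it is (rate on NGM282 − rate on placebo) × effect. The pooled value is p times that.

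| Case | Experienced | Naive | Pooled |
|---|---|---|---|
| Low | (0.60 − 0.20)×(−20) = −8 | 0 | 0.30×(−8) = −2.4 mg/dL |
| High | (0.80 − 0.30)×(−40) = −20 | 0 | 0.45×(−20) = −9.0 mg/dL |

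**Step 2: does a cofactor remove the averaging?** No. Simulating 42 v 21 under the high case gave about -9 mg/dL both without and with a statin-status main effect. In SD units, with a true difference of -1 in experienced and 0 in naive subjects and p = 0.32, the estimates were -0.32 and -0.31, against a weighted average of -0.32. Only results by stratum, or an arm-by-status term, separate the regimens.

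**Step 3: precision.** Omitting a baseline binary factor multiplies the variance by 1 + p(1−p)d², where d is the experienced-minus-naive difference in EOS change, in residual SDs, after the other covariates. At p = 0.32:
- d = 0.5: √(1 + 0.2176×0.25) = 1.027
- d = 1: √(1 + 0.2176) = 1.103

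The standard error (SE) is thus 0% to 10% larger for d from 0 to 1. If d = 0, the added term costs about 1% in SE.

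The simulation was repeated in mg/dL (residual SD 22, experienced baseline LDL-C 15 lower, baseline slope -0.3). The change in the EOS 95% CI half-width from adding the cofactor ran from about 1% wider (effect 0) to 0.9% narrower (low case, -20) and about 9% narrower (high case, -40). At Week 24, a simulation over similar ranges gave changes of -1.0% to +1.5%, which is negligible.

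**Step 4: chance imbalance.** Statin status is not a randomisation stratum. At p = 0.32 and 50 v 25, the SD of the difference in share experienced is √(0.32×0.68×(1/50 + 1/25)) = 0.114, so the 95% range is about ±22 percentage points. This can shift a single trial's estimate but averages to zero.

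**Step 5: what stratum results can show.** At p = 0.32 and 42 v 21, in residual SDs:
- experienced: √(1/13.44 + 1/6.72) = 0.47
- naive: √(1/28.56 + 1/14.28) = 0.32
- overall: √(1/42 + 1/21) = 0.27
- interaction: √(0.47² + 0.32²) = 0.57, or about 12.5 mg/dL at SD 22

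The differences between strata in Step 1 were -8 and -20 mg/dL, so the interaction is descriptive rather than a powered test.

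**The case against.** The SAP does what the protocol prescribes. Protocol 12.9.3 stratifies this cohort's secondary analyses by fibrosis stage, which is also the randomisation stratum, and it only permits further cofactors. SAP 4.2 lists lipid changes to EOT, where statin status adds nothing. Parts of SAP 8.2 and 8.3 and the table index are redacted, the mock-ups are separate, and the statin algorithms are not shown, so a by-statin display may exist. All of this stands. The point is therefore a missed improvement and not a contradiction, and it concerns EOS. The 8.2.5 model statement itself is readable and has no statin term.

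Several stronger readings are tempting, and the documents do not support them:

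- **That baseline status decides who is on rosuvastatin at EOS.** Naive status means off it. Experienced status is necessary but not sufficient: Protocol 9.6.3 lets the site be told to keep current therapy, and 9.6.9 dispenses at Week 24 only to experienced subjects taking therapy.
- **That the missing covariate causes the averaging, or that adding it cures it.** The averaging comes from the design and the single contrast (Step 2).
- **That the omission biases the comparison or inflates type I error.** It does neither for the comparison of assigned regimens.
- **That precision is certainly lost.** Baseline lipid is already in the model. A gain needs statin status to predict change beyond it, and no figure in the documents settles that.
- **That fibrosis-stage summaries should give way to statin status.** That would depart from Protocol 12.9.3.
- **That diabetic status should likewise be added for the glycaemic endpoints.** Protocol 12.9.2 confines that cofactor to the double-blind cohort, and no gain has been computed.

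**Conclusion.** The concern holds as a matter of interpretation. The EOS lipid contrast in SAP 8.2.5 is a valid comparison of assigned regimens, but it pools subjects off rosuvastatin with subjects who may be on it. With no residual NGM282 effect it would average about -2 to -9 mg/dL of LDL-C in favour of NGM282, from continued rosuvastatin alone. That range rests wholly on the assumed shares, uptake rates and statin effect listed above, and it would be zero if uptake among experienced subjects were equal in the two arms. The precision argument is secondary and conditional: from about a 1% loss to a 9% gain in EOS half-width for assumed effects of 0 to -40 mg/dL, and nothing material at Week 24. The change is worth making because the data are already collected, the protocol allows it, and it serves the rosuvastatin objective.

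**What to change.** In SAP 8.2.5:

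1. Add baseline statin status (naive/experienced) as a cofactor in the ANCOVA for total cholesterol, LDL-C, HDL-C and lipoprotein particles.
2. Present Week 24 and EOS changes by arm and baseline statin status, with the arm-by-statin-status interaction and 95% CIs, in addition to the fibrosis-stage summaries. State that these results are descriptive.
3. State that the pooled EOS contrast compares assigned regimens, including the statin rules, and does not measure recovery after NGM282 alone.
4. Do not adjust for on-study rosuvastatin use, which arises after randomisation and can be affected by treatment.

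Separately, reconcile who continues rosuvastatin after Week 24. The rosuvastatin footnote to Protocol Table 4, repeated in SAP Appendix A, reads as all subjects on a statin at screening, while Protocol 9.6.9 limits dispensing to experienced subjects taking therapy.

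The cost is SAP wording, one degree of freedom for the cofactor (about 1% in SE if statin status is not prognostic), and stratum estimates that will be imprecise, especially in experienced subjects. No new data are needed.
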